## 8.6 Deviations to Statistical Plan

Any deviation from the statistical plan discussed above will be documented in the study report.

## 9. MONITORING

3M, as sponsor of this study, is responsible for ensuring the proper conduct of the study with regard to protocol adherence and validity of the data recorded. 3M has therefore assigned a study monitor to this study. The progress of the study will be monitored by:

- Periodic on-site review
- Ongoing review of electronic documentation [REDACTED]
- Telephone and e-mail communications
- Review of source documents

[REDACTED]

The Investigator or designee will give the 3M study monitor direct access to source documents that support data on the eCRFs and make available such records to authorized 3M, quality assurance, IRB/EC, and regulatory personnel for inspection and/or copying.

## **10. QUALITY CONTROL AND QUALITY ASSURANCE**

3M is responsible for implementing and maintaining quality assurance and quality control systems through written standard operating procedures (SOPs) to ensure that this study is conducted and data are generated, documented and reported in compliance with the protocol, GCP and regulations cited in Section 1.5 of this protocol. Study monitoring is carried out to accomplish this.

## **11. ETHICS**

This study will be conducted in accordance with the principles that have their origin in the Declaration of Helsinki, 21 CFR 50 (Informed Consent) and 56 (IRBs). The study will start only after approval of the protocol and consent form by the IRB/EC. The approval letter or notice must contain the IRB/EC name, meeting date, and sufficient information to identify the protocol and informed consent by name and number that were reviewed. 3M, prior to study initiation, must receive a copy of the IRB/EC approval letter.

## **12. DATA HANDLING AND RECORD KEEPING**

### **12.1 Study Personnel**

Prior to study initiation, the Investigator must provide 3M with a signed Form FDA 1572. This form identifies all sub-investigators who will be assisting the Investigator in the conduct of the study. The Investigator will provide a log of signatures/initials and delegation of responsibility log prior to study initiation.

### **12.2 Pre-Study Documentation Requirements**

Prior to study initiation, the Investigator must provide 3M with the following documents:

- Signed protocol including any amendments in place prior to study initiation
- *Curriculum vitae* for the Investigator and any sub-investigators
- IRB/EC approved consent form
- IRB/EC study approval letter
- IRB/EC name, location and membership list
- IRB/EC certification
- Signed Form FDA 1572
- Financial Disclosure
- Signed research agreement

### **12.3 Completion and Return of Case Report Forms**

Electronic data capture (eDC) software will be used for this study. Data may be recorded onto data collections sheets prior to data entry or may be entered directly into the eDC system. Microbiological count data will be recorded onto DCSs prior to entry into the eDC system. If a correction is required, a single line must be drawn through the error. The person making the correction will initial, date, and provide a reason for the error (if not self-evident). Once the forms are completed, the monitor will review the case report form (CRF) to assure accuracy and completeness.

### **12.4 Final Report**

[REDACTED]

The Investigator will submit the Final Report to 3M and the IRB/EC.

### **12.5 Records, Reports and Retention Requirements**

Study records must be kept until 3M provides notification that the documents can be destroyed. This may extend beyond the 2 years required by law. In order to comply with regulatory requirements, the Investigator must arrange for the retention of all study records for 2 years following the date a marketing application is approved for the drug and indication investigated, or if no application is filed, until 2 years after completion/termination of the study [see 21 CFR 312.62 (c) and 21 CFR 812.140(d)].

Records to be retained in the Investigator study file include, but are not restricted to:

- Signed study protocol, amendments, deviations
- Applications to the IRB/EC
- IRB/EC approval of protocol, consent form, authorization form and amendments to any of these documents
- Signed consent forms
- Case report forms and/or data collection forms
- Adverse event reports
- Records of receipt, use, or disposition of the investigational drug
- Correspondence relating to the study
- Investigator Brochure
- Statement of Investigator
- Financial disclosure documents
- Final Report

[REDACTED]

## 14. APPENDICES

[figure not shown]
### 14.1 Study Flow Diagrams

#### Informed Consent/Wash out and Screening Day

[REDACTED]

## Treatment Day

## 14.2 Study Product Application Instructions

Figure 4 is a bar chart showing the effect of the number of training samples on the error rate. The y-axis is labeled 'Error rate' and ranges from 0.0 to 0.4. The x-axis is labeled 'Number of training samples' and has logarithmic ticks at  $10^1$ ,  $10^2$ ,  $10^3$ ,  $10^4$ , and  $10^5$ . The error rate is high for small numbers of training samples (around 0.35 for  $10^1$  and  $10^2$ ) and decreases as the number of training samples increases, reaching a low error rate (around 0.05 for  $10^5$  and  $10^6$ ). The error rate is also low for  $10^3$  and  $10^4$  training samples, around 0.08 and 0.12 respectively.

Number of training samples	Error rate
$10^1$	0.35
$10^2$	0.35
$10^3$	0.08
$10^4$	0.12
$10^5$	0.05
$10^6$	0.05

### 14.3 Confirmation of Release & Receipt of Clinical Supplies

The image consists of several horizontal black bars of varying lengths and positions. The bars are set against a white background. The first bar is the longest and is positioned near the bottom. Above it, there are three shorter bars. To the right of the second bar, there is a small, separate black square. Further up, there are two more horizontal bars, with the second one being longer than the first. At the very top, there is a long horizontal bar. The overall pattern suggests a step function or a series of discrete events plotted against a horizontal axis.

**Health Care  
[name]**

Page 31 of 42

Status: Release

Version: 1

Issue Date: 05/19/2017 11:37:31 AM CDT

## 14.4 Study Product Disposition Form

## 14.5 Subject Instructions

The figure consists of 20 horizontal bars, each composed of a black segment and a white segment. The black segments represent the data values, and the white segments are of uniform length. The bars are arranged vertically, with a thin horizontal line separating the groups of bars.

Bar	Black Segment (Data Value)	Total Length
1	~18	~20
2	~15	~20
3	~18	~20
4	~15	~20
5	~18	~20
6	~15	~20
7	~18	~20
8	~15	~20
9	~18	~20
10	~15	~20
11	~18	~20
12	~15	~20
13	~18	~20
14	~15	~20
15	~18	~20
16	~15	~20
17	~18	~20
18	~15	~20
19	~18	~20
20	~15	~20

#### 14.7 Test Site Diagrams

#### 14.8 Skin Irritation Rating Scale

■ [REDACTED]

[REDACTED]

## 14.9 Protocol for Neutralization Validation

### 14.9.1 Background

In order to accurately assess the efficacy of an antimicrobial product, it is necessary to completely inactivate the antimicrobial agent at the time point being evaluated. Inadequate neutralization will allow killing or inhibition of the microorganisms to continue beyond the specified contact time, resulting in an overestimation of antimicrobial activity.

Standard sampling solution (SSS) is a buffered detergent solution that is commonly used in studies where microbial sampling of skin is conducted. Neutralizers have been added to inactivate the antimicrobial, CHG, present in the active study products. [REDACTED]

[REDACTED] The effectiveness and nontoxicity of these neutralizer systems must be assessed to demonstrate that there is no effect on the growth of microorganisms and that the antimicrobial ingredient is inactivated.

The density of normal human skin flora generally ranges from  $10^2$  to  $10^5$  CFU/cm^2 depending on the body site. However, since significant neutralizer or toxic effects are more easily detected at a lower cell density, the efficacy and toxicity of these neutralizers will be assessed against a lower bacterial concentration.

This is an *in vivo* test where the active study products are applied to the skin using the same application instructions used for the study (Appendix 14.2). Scrub cup samples are collected and inoculated with low levels of [REDACTED]

[REDACTED] Two contact times after inoculation will be evaluated: immediately (<1 minute) and [REDACTED] minutes (to test for residual antimicrobial activity between sample collection and the time of plating).

### 14.9.2 Objective

The objective of this assay is to determine the ability of the sampling solutions to completely neutralize the active ingredients contained in [REDACTED] when applied to the abdomen of test subjects without exhibiting toxicity to the test organisms.

[figure not shown]
### 14.9.3 Subject Entry Criteria

Six subjects will participate in this study. Subjects must meet the inclusion and exclusion criteria in Sections 4.1 and 4.2 of the protocol to which this neutralizer validation is attached, except for the baseline bacterial count, the 72-hour exclusion from showering/bathing, and the length of the washout period. The neutralization subjects do not require a minimum baseline count and they only need to avoid topical and systemic antimicrobials for 7 days (not 14 days) prior to Treatment Day. Subjects will be asked to sign the Informed Consent Form and provide information on demographics and inclusion/exclusion criteria before beginning the 7-day washout period. When subjects return to begin their participation in the study they will again be asked to provide information relative to inclusion/exclusion criteria. If they meet all [REDACTED]

inclusion/exclusion criteria, they may be enrolled [REDACTED].

Each subject will receive the active study product, [REDACTED], which will be applied to the test area on the abdomen. See diagram below.

#### Neutralization Test Area Diagram

#### 14.9.4 Test Organism

The test organisms for this study are [REDACTED]

#### 14.9.5 Study Products

[REDACTED] Surgical Solution, Tint, 26-mL applicator.

#### 14.9.6 Materials, Supplies and Equipment

- Subject Informed Consent forms, IRB/EC-approved

#### 14.9.7 Study Procedures

##### 14.9.7.1 Preparation of Inoculum

One day prior to beginning the neutralization assay, the test organisms from a stock culture slant or from a lyophilized vial will be inoculated on TSA. The plates will be incubated for 24 [redacted] hours at  $35^{\circ} \pm 2^{\circ}\text{C}$ .

Immediately prior to initiating the neutralization assay, an inoculum suspension for each test organism will be prepared in PBW solution from the overnight culture on the TSA plate, and the concentration adjusted to approximately  $10^8 - 10^9$  CFU/mL.

Dilute the inoculum suspension with PBW to achieve an appropriate concentration (approximately  $10^4$  CFU/mL) for inoculation of the test samples. The density of the test inocula must be verified by direct plating at the beginning and end of the study.

##### 14.9.7.2 Preparation of Test Area and Post-Prep Sampling

Neutralization samples will be evaluated on the abdomen. Each subject will be treated with the study product in the abdominal test area.

The abdominal test area will be marked using a sterile 1.5" x 5" template [redacted]. A 1.5" x 5" area will be delineated on one side of the body containing two 1" x 1" sampling sites, yielding 2 samples per subject. The tube from one sampling area will be inoculated with [redacted] and the other will be inoculated with [redacted].

After the test area is marked, the test area will be prepped with three 70% isopropyl alcohol swabs for a total of 1 minute and allowed to dry for 3 minutes.

The test area will be treated with the study product, according to the instructions provided in Appendix 14.2 of the protocol to which this neutralizer validation is attached.

Samples will be collected, using the scrub cup technique, at 10 minutes [redacted] post-prep. Post-prep timing begins upon completion of study product application, including the 3-minute drying time. The sampling technique is described in Section 6.2.1.1 of the protocol to which this neutralizer validation is attached.

Residual product should be removed from test area after sample collection is complete [redacted].

Each pooled sample (~6 mL) will be capped tightly [redacted] followed by vortex mixing for 30 seconds. Five mL will be transferred to a clean tube and immediately inoculated with 100  $\mu\text{L}$  of the appropriate [redacted].

diluted inoculum (Section 14.9.7.1 of the neutralization validation). This will yield an organism concentration of ~20 – 200 CFU/mL.

Immediately (<1 minute) and [REDACTED] minutes [REDACTED] post-inoculation, [REDACTED] aliquots of the inoculated samples will be pour-plated in triplicate using TSA+N. Plates will be incubated inverted at  $35 \pm 2^{\circ}\text{C}$  for 48 [REDACTED] hours.

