##### Numbers Control (NC):

Add 100  $\mu\text{L}$  of the appropriate diluted inoculum to a tube containing 5 mL PBW to yield final inoculum concentrations of ~20-200 CFU/mL. [REDACTED]

[REDACTED] Pour-plate triplicate [REDACTED] aliquots immediately (<1 minute) and [REDACTED] minutes [REDACTED] post-inoculation in the same manner as 14.9.7.2, except using TSA without neutralizers.

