#### **14.9.8 Control of Bias**

Bias is controlled by internal controls and triplicate plating.

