#### **14.9.9 Data Evaluation**

Recovery for each of the samples will be expressed as  $\log_{10}$  CFU/mL.

Neutralizer Effectiveness:

If the mean  $\log_{10}$  CFU/mL of the sample is not more than 0.3  $\log_{10}$  less than the mean  $\log_{10}$  CFU/mL of the NC, the neutralization will be considered effective.

- Mean  $\log_{10}$  CFU/mL from NC – Mean  $\log_{10}$  CFU/mL from sample (use corresponding time points)

Neutralizer Toxicity:

If the mean  $\log_{10}$  CFU/mL of the TC is not more than 0.3  $\log_{10}$  less than the mean  $\log_{10}$  CFU/mL of the NC, the sampling solutions will be considered non-toxic.

- Mean  $\log_{10}$  CFU/mL from NC – Mean  $\log_{10}$  CFU/mL from TC (use corresponding time points).

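### The visible neutralization validation compares a spiked skin wash with spike-only controls under a one-sided rule and never checks native background, so surviving flora could mask incomplete neutralization

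*Combined protocol and SAP*

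**What the plan says.** **Sample.** Section 14.9.3 enrols six people ("Six subjects will participate in this study") and exempts them from the baseline criterion: "The neutralization subjects do not require a minimum baseline count". No maximum is set. Under 14.9.7.2, "the test area will be prepped with three 70% isopropyl alcohol swabs for a total of 1 minute" and left to dry for 3 minutes. The product is then applied and two cup-scrub samples per subject are taken 10 minutes post-prep, one per test organism. From each pooled wash of about 6 mL, "Five mL will be transferred to a clean tube and immediately inoculated with 100" µL of diluted inoculum, for a stated 20–200 CFU/mL.

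**Controls.** Section 14.9.7.3 names two. The numbers control (NC) adds the inoculum "to a tube containing 5 mL PBW to yield final inoculum concentrations of" about 20–200 CFU/mL. The toxicity control does the same in fresh sampling solution. Both are spiked and neither contains skin material.

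**Decision rule.** In 14.9.9, if the sample mean is not more than 0.3 log10 below the mean log10 "CFU/mL of the NC, the neutralization will be considered effective". The formula is NC minus sample, with no background term and no upper limit.

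**Bias and flora.** Section 14.9.8 reads "Bias is controlled by internal controls and triplicate plating". Section 14.9.1 says "The density of normal human skin flora generally ranges from" 10² to 10⁵ CFU/cm² depending on body site, and gives no abdominal figure.

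**The concern.** The sample count is surviving spike plus any surviving native organisms. The NC count is spike only. Because the rule looks only for a shortfall against the NC, native colonies can move the result in one direction, toward a pass. Triplicate plating reduces random error but cannot remove a systematic addition. Section 14.9.1 chooses a low spike because neutralizer effects are easier to see at low density, but a low spike is also the one a small background distorts most.

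The same section warns that poor neutralization overstates antimicrobial activity. According to 6.2.1.3, this validation is how neutralizer effectiveness is tested before Treatment Day. The main study is uncontrolled (3.1) and rests on a mean 2.0 log10 reduction at all three locations (8.2.1), so no comparator arm would reveal such a bias.

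**Working it through.** **Plan's own figure.** Inoculum of about 10⁴ CFU/mL (14.9.7.1), 0.1 mL into 5 mL: 10⁴ × 0.1 / 5.1 = 196 CFU/mL, the top of the stated range. The bottom needs an inoculum near 10³: 10³ × 0.1 / 5.1 = 19.6. The stated range is reproduced.

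**Inputs from the documents.** Sample volume about 6 mL, 5 mL spiked, tolerance 0.3 log10, i.e. a pass fraction of 10^−0.3 = 0.501.

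**Assumptions.** Cup area is not visible; I use 5 cm², with a range of 3.8 to 6.45 cm² (6.45 being the full 1 inch by 1 inch site). Residual flora is not given; I show 1, 10 and 100 CFU/cm². For example, 10³ CFU/cm² leaves 10 after a total reduction of 2 log10 and 1 after 3 log10.

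**Model.** Let N be the spike and R the native survivors, both in CFU/mL in the tube, and S the true fraction of spike recovered. R = residual × area / 6 × 5/5.1, so 10 CFU/cm² with 5 cm² gives 8.17 CFU/mL.

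- (a) Native cells unaffected by un-neutralized agent: a pass needs S ≥ 0.501 − R/N.
- (b) Native cells killed as hard as the spike: a pass needs S ≥ 0.501 / (1 + R/N).

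The largest true loss that still passes is −log10 of that S. At N = 196 and R = 8.17, (a) gives 0.501 − 0.042 = 0.459, or 0.34 log10; (b) gives 0.501 / 1.042 = 0.481, or 0.32.

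| Residual, CFU/cm² (5 cm² cup) | N = 20: (a) / (b) | N = 196: (a) / (b) |
|---|---|---|
| 0 | 0.30 / 0.30 | 0.30 / 0.30 |
| 1 | 0.34 / 0.32 | 0.30 / 0.30 |
| 10 | 1.03 / 0.45 | 0.34 / 0.32 |
| 100 | no limit / 1.01 | 1.07 / 0.45 |

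No limit means that native colonies alone would satisfy the rule.

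**Sensitivity to cup area at 10 CFU/cm².** Over 3.8 to 6.45 cm², N = 196 gives 0.33–0.35 (a) and 0.31–0.32 (b). N = 20 gives 0.72 to no limit (a) and 0.42–0.48 (b).

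**Native flora that turns a 60% loss into a pass.** A 60% loss is −log10(0.40) = 0.40 log10 and should fail. Under (a), R = N × (0.501 − 0.40) = 0.101N. Under (b), R = N × (0.501/0.40 − 1) = 0.253N.

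| Spike | (a) CFU/mL | (b) CFU/mL | On skin, 3.8–6.45 cm² cup: (a); (b), CFU/cm² |
|---|---|---|---|
| 20 | 2.0 | 5.1 | 1.9–3.3; 4.8–8.1 |
| 196 | 20 | 50 | 19–32; 47–80 |

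**The case against.** The design already works against native flora: a one-minute alcohol swab, a drying period, a CHG/alcohol product and a 10-minute wait all precede sampling. No figure in the documents shows that material flora survives this. The waiver in 14.9.3 removes a minimum count, and the 72-hour bathing restriction is lifted too; both admit low-flora subjects and neither is evidence of a high background. At the nominal inoculum a residual of 10 CFU/cm² barely moves the limit. Native cells share the tube with any un-neutralized agent, so (b) may be nearer the truth, and it raises the flora needed to mask a 60% loss 2.5-fold. Parts of 14.9.7.2 to 14.9.7.4 and both organisms are redacted, so a blank, a counting rule or a way of telling colonies apart may exist out of view.

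All of this stands as a limit on size. A reader might infer that the samples do contain surviving flora, that the plan has no blank, or that post-prep counts in the main study are overstated. The documents support none of these: the first is not shown, the second cannot be judged through the redactions, and the third would need a real neutralizer failure together with enough surviving flora relative to the spike.

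What the objection leaves is the comparison itself. The visible formula in 14.9.9 uses only sample, NC and toxicity control, so even a blank hidden in redacted text would not enter it as written. The pre-swab lowers the background; nothing visible verifies the result.

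**Conclusion.** The concern holds as a gap in verification. Native survivors, if any, can only help the sample pass, and the visible text neither measures nor subtracts them. The size depends on spike level and residual flora, neither of which the documents fix. With a 5 cm² cup and 10 CFU/cm² remaining, the effective tolerance widens by about 0.02–0.04 log10 at the nominal spike but by about 0.15–0.73 at the low end of the accepted range. With 1 CFU/cm² remaining it widens by at most 0.04 (0.05 with the largest assumed cup). At the nominal spike, substantial masking needs tens to about 100 CFU/cm². Cup area, residual flora and the two kill models are assumptions. This is an inexpensive improvement to the assay; it does not show that the neutralizer fails or that the main study's reductions are biased.

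**What to change.** In 14.9.7.2, plate the roughly 1 mL left from each pooled sample (about 6 mL less the 5 mL transferred) unspiked on TSA+N, with the same incubation. State when it is plated relative to the two contact times.

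In 14.9.9, subtract this native count, scaled to the plated volume and the 5/5.1 dilution, from the spiked count before taking log10. Report the native count. Flag samples where it is a material share of the NC or where recovery lies well above the NC. If the blank reflects the native cells surviving in the spiked tube, subtraction restores the 0.30 log10 limit in expectation whatever the flora. If a redacted part already provides a blank, only the change to the 14.9.9 formula is needed.

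Do not add a rule to repeat samples with high background. A repeat would need new procedures on subjects whose two marked sites are both used. A cut-off such as 10% of the NC would rest on about 2 colonies on a 1 mL plate at the 20 CFU/mL spike (0.10 × 20 = 2).

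Cost: about 12 plates (6 subjects × 2 samples) from liquid already collected, a few sentences in 14.9, and slightly noisier sample counts because a single-plate count is subtracted. No added subject procedure.

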#### **14.9.7.3 Numbers Control and Toxicity Control**

This testing will be performed in triplicate.

##### Numbers Control (NC):

Add 100  $\mu\text{L}$  of the appropriate diluted inoculum to a tube containing 5 mL PBW to yield final inoculum concentrations of ~20-200 CFU/mL. [REDACTED]

[REDACTED] Pour-plate triplicate [REDACTED] aliquots immediately (<1 minute) and [REDACTED] minutes [REDACTED] post-inoculation in the same manner as 14.9.7.2, except using TSA without neutralizers.

##### Toxicity Control (TC-MSS):

Add [REDACTED] 5.0 mL SSS [REDACTED]

[REDACTED] to a clean tube. Add 100  $\mu\text{L}$  of the appropriate diluted inoculum to the 5-mL tube to yield final inoculum concentrations of ~20-200 CFU/mL. Pour-plate triplicate [REDACTED] aliquots immediately (<1 minute) and [REDACTED] minutes [REDACTED] post-inoculation in the same manner as 14.9.7.2.

These controls will provide assurance that the test organisms are not adversely affected by the treatments or the sampling procedures.

#### **14.9.7.4 Enumeration**

[REDACTED] Enumerate plates and calculate CFU/mL for each sample. Convert data to  $\log_{10}$  CFU/mL.

#### **14.9.8 Control of Bias**

Bias is controlled by internal controls and triplicate plating.

